4.7.1.5 Planned Analyses

Interim Analysis: No interim analyses are planned.

Week 24 Analysis: Primary analysis will be carried out once all subjects have completed week 24 visit (excluding Follow-up) or have withdrawn from the study. No one directly involved with the

conduct of the study will see the unblinded data before the completion of the trial, in order to avoid biasing the remaining data of the study.

Final Analysis: The final analysis will be performed when the last subject has completed the study (i.e. completed the safety follow-up or has withdrawn from the study).

4.7.1.6 Examination of Subgroups

To evaluate the consistency of treatment effects, subgroup analyses will be explored for the primary and selected secondary efficacy endpoints based on:

- Region (Europe, North America, Asia-Pacific)
- Age (18-65 or >65)
- Gender (Male, Female)
- Race (White, Black, Asian, Other)
- Baseline IGA (3 or 4)
- Baseline EASI (\leq median or $>$ median)
- Intrinsic or extrinsic AD (based on IgE and eosinophil counts)

Subgroup analyses will be explored for safety endpoints (e.g., AEs) based on:

- Age (18-65 or >65)
- Gender (Male, Female)
- Race (White, Black, Asian, Other)

If the number of subjects in a subgroup is too small, subgroups may be pooled for analyses.

4.7.2 Primary Efficacy Endpoint

The primary variable for the assessment of efficacy is the percent change from baseline in EASI at week 24.

The primary endpoint will be analyzed using a MMRM approach, including terms of treatment group, and baseline IGA severity for ITT and PP populations. Visit will be fitted as a categorical variable, with the effect of treatment group and baseline IGA varying at each visit (i.e., interaction between treatment group and visit and interaction between baseline IGA and visit). The corresponding baseline values of the response variable will be included as a covariate in the model. An unstructured (UN) covariance matrix for repeated measures within a subject will be used to model the within-subject errors in the analysis, unless there are issues related to convergence. If the UN covariance matrix leads to non-convergence, then Akaike's information criterion (AIC) will be used to select the best covariance matrix among autoregressive, compound symmetric, and Toeplitz. The Kenward-Rogers adjustment will be used with restricted maximum likelihood (REML) to make proper statistical inferences. Denominator degrees of freedom will be estimated using approximation of Kenward-Rogers. A linear contrast will be used, within the MMRM framework, to estimate difference between each nemolizumab

dose regimen and placebo. LSmeans with 95% CI and the corresponding statistical p-value will be presented for the treatment difference between each nemolizumab dosing regimen and placebo at a given visit.

Other covariates may be explored and will be added into the model, if appropriate.

Dose Response Analysis: MCP-Mod approach will be applied using a set of candidate dose-response models (see table below) to test for a dose-response relationship via model-associated statistics. The analysis will be performed using the available R software package “MCPMod” or any other available software.

Linear	E _{max}	Sigmoid E _{max}
Linear	1. ED50=10mg 2. ED50=30mg	1. ED50=10mg, H (Hill)=1 2. ED50=10mg, H (Hill)=2 3. ED50=10mg, H (Hill)=3 4. ED50=15mg, H (Hill)=2 5. ED50=20mg, H (Hill)=4 6. ED50=30mg, H (Hill)=2

ED50=dose produces 50% of maximum effect

Sensitivity analysis: The robustness of the primary analysis will be investigated by performing the sensitivity analyses as described in 4.7.1.3.

Subgroup analysis: The homogeneity of the treatment effect for a number of important subgroups will be investigated as described in 4.7.1.6.

Least square mean (LSmean) of treatment difference and the respective 95% CIs will be used for all subgroup comparisons at week 24. In addition, the p-values for the interaction of the treatment groups and the subgroups will also be provided, wherever appropriate. The LSmean of treatment difference, respective 95% CI and interaction p-values will be based on ANCOVA including terms of treatment group, the corresponding baseline value, subgroup factor and interaction between treatment group and subgroup.

A by-subject listing of the primary efficacy data will be provided. In addition, line plots showing the mean percent change from baseline in EASI over time within each treatment group will be produced for ITT and PP populations

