Quality-of-life (QoL) assessment:	
 - Dermatology Life Quality Index (DLQI) at baseline, weeks 2, 12 & 24 - Hospital Anxiety and Depression Scale (HADS) at baseline, weeks 12 & 24 - Missed work/school days to be recorded at weeks 4, 8, 12, 16, 20 & 24 - EuroQoL 5-Dimension (EQ5D) at baseline and week 24

Principal statistical method:
	
Primary inference for all the efficacy analyses will be based on the intent-to-treat (ITT) population at the week 24 endpoint. The primary endpoint will be analyzed using a Mixed-effect Model for Repeated Measures (MMRM) approach, including terms of treatment group, and baseline IGA severity. Visit will be fitted as a categorical variable, with the effect of treatment group and baseline varying at each visit.
 
Continuous secondary efficacy endpoints will be analyzed in a similar manner to the analysis of the primary endpoint. All categorical efficacy endpoints will be analyzed using a stratified Cochran Mantel-Haenszel test.
 
Multiple comparison procedures-modeling (MCP-Mod) approach will be applied using a set of candidate dose-response models to test for a dose-response relationship via model-associated statistics.
 
Exposure-response modeling will also be conducted for the primary endpoint of EASI percentage change from baseline at week 24, and for percentage change in pruritus NRS at week 4.
 
Primary inference for all the safety analyses will be based on the safety population. A summary of safety endpoints (treatment-emergent adverse events [TEAE], vital signs, laboratory parameters and ECG etc.) will be presented by treatment group.
 
To impute the missing values for continuous endpoints, mixed-effect MMRM approach will be used for the primary and secondary endpoints. All missing values will be treated as a non-responder for binary endpoints. All efficacy data, except in observed case analysis, will be set to missing after rescue medication is used.

Sample size:
	
Sample size is estimated using MCP-Mod approach by selecting a set of candidate dose response shapes based on primary endpoint response (percent change in EASI). Assuming placebo response of 35%, standard deviation 45% and a maximum treatment difference of 30%, 50 subjects per arm will provide at least 90% power to detect a statistically significant dose-response for at least one model at 1-sided significance level of 0.025.

Table 1 Clinical trial schematic

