9.1.5.2.1 Primary efficacy analysis

The primary endpoint is percentage change in EASI score from baseline to week 24.

The primary endpoint will be analyzed using a MMRM approach, including terms of treatment group, and baseline IGA severity. Visit will be fitted as a categorical variable, with the effect of treatment group and baseline IGA varying at each visit. An unstructured covariance will be used to model the within-patient errors in the analysis. A linear contrast will be used, within the MMRM framework, to estimate difference between nemolizumab dose levels and placebo. Other covariates may be explored and will be added into the model, if appropriate. Treatment difference for each nemolizumab dosing regimen versus placebo will be estimated along with associated 95% confidence intervals will be presented.

Multiple comparison procedures-modeling (MCP-Mod) approach will be applied using a set of candidate dose-response models to test for a dose-response relationship via model-associated statistics.

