4.7.1.2 Adjustments for Covariates

The primary efficacy analysis will be adjusted for the following baseline covariates:

- Baseline IGA severity (the stratification factor)
- Baseline EASI

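### The primary MMRM fits one baseline-EASI slope across all eight visits; a baseline-by-visit term would protect week-24 precision at almost no cost

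*SAP*

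**What the plan says.** The model is described in four places.

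- **Protocol synopsis, Principal statistical method.** An MMRM "including terms of treatment group, and baseline IGA severity", followed by "Visit will be fitted as a categorical variable, with the effect of treatment group and baseline varying at each visit".
- **Protocol 9.1.5.2.1.** The same model, with the second sentence reading "Visit will be fitted as a categorical variable, with the effect of treatment group and baseline IGA varying at each visit". The covariance is unstructured, and other covariates may be added if appropriate.
- **SAP 4.7.1.2.** "The primary efficacy analysis will be adjusted for the following baseline covariates": baseline IGA severity and baseline EASI.
- **SAP 4.7.2.** The visit interactions are written out as "interaction between treatment group and visit and interaction between baseline IGA and visit". The next sentence adds the baseline EASI term: "The corresponding baseline values of the response variable will be included as a covariate in the model". No interaction of that term with visit is named.

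Read as written, baseline EASI has a single slope over weeks 1, 2, 4, 8, 12, 16, 20 and 24. SAP 4.7.3 and 4.9.3 apply the same approach to pruritus NRS, sleep disturbance NRS, SCORAD, DLQI and HADS, each with its own baseline value.

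**The concern.** A single slope in an MMRM is a weighted average of the visit-specific slopes, with weights set by the inverse covariance matrix. Those weights favour the early, less variable visits. At week 1, percent change in EASI may have had little time to become related to baseline; by week 24 the relation may be stronger. The pooled slope would then under-adjust at the one visit that carries the primary inference, and part of the benefit of putting baseline EASI in the model would be lost.

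The same applies to the reused models. For absolute change, the slope on baseline at visit t is ρ_t·(σ_t/σ_0) − 1, where ρ_t is the correlation of the score at visit t with its baseline. With equal SDs, a fall in ρ_t from 0.8 to 0.5 (assumed) moves the slope from −0.2 to −0.5. A constant slope over visits is therefore not the natural default for these endpoints.

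**Working it through.** **1. The plan's own figure.** From SAP 4.10: maximum difference 30, SD 45, 50 per arm, one-sided 0.025.

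- Pairwise check (normal approximation): SE = 45·√(2/50) = 9.0; 30/9.0 = 3.333; 3.333 − 1.960 = 1.373; power = 0.915.
- MCP-Mod maximum-contrast test (doses 0/10/30/90, the nine listed shapes scaled to 30 at 90 mg, 196 df, simulated): power 0.929 to 0.983. The stated 90% is reproduced.

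**2. Formula for the loss.** Let r be the correlation of baseline EASI with percent change at week 24, and c the pooled slope as a fraction of the week-24 slope. Then

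SE ratio (pooled / visit-specific) = √{ [1 − r² + r²(1 − c)²] / (1 − r²) }.

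For r = 0.3:

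- c = 0.5: √[(0.91 + 0.0225)/0.91] = 1.012
- c = 0 (no EASI adjustment in effect): √[(0.91 + 0.09)/0.91] = 1.048
- c = −0.33: √[(0.91 + 0.159)/0.91] = 1.084

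**3. What c would be.** The pooled slope is (1′Σ⁻¹β)/(1′Σ⁻¹1), where β holds the visit slopes and Σ is the residual covariance including the misfit, iterated to convergence. Assumed: eight visits, SD rising evenly from 25 to 45, correlation rising in proportion to week, complete data, no IGA term.

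| Within-subject correlation | c | r = 0.1 | r = 0.2 | r = 0.3 |
|---|---|---|---|---|
| AR(1), 0.7 between adjacent visits | 0.23 | +0.3% | +1.2% | +2.9% |
| Constant 0.5 | −0.06 | +0.6% | +2.3% | +5.4% |
| Constant 0.7 | −0.33 | +0.9% | +3.6% | +8.4% |

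With a high, constant correlation the later visits can take negative weight. The pooled slope then has the opposite sign to the week-24 slope, which is what produces the upper ends. A constant correlation above 0.7 would push them further.

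**4. Simulated MMRM.** Unstructured covariance, IGA-by-visit in the model, 50 per arm, 400 runs per scenario, complete data. Mean model SE of 90 mg versus placebo at week 24:

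| r | No EASI | One slope | Slope by visit | Loss |
|---|---|---|---|---|
| 0.1 | 9.04 | 9.03 | 9.02 | 0.1% |
| 0.2 | 9.25 | 9.20 | 9.08 | 1.4% |
| 0.3 | 9.51 | 9.40 | 9.07 | 3.7% |

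At r = 0.3 the single slope keeps (9.51 − 9.40)/(9.51 − 9.07) = 25% of the available gain. A loss of 3.7% is a variance ratio of 1.037² = 1.075, or 50·(1 − 1/1.075) ≈ 3.5 subjects per arm. With 25% random dropout the loss was 0.1% (r = 0.1) and 1.3% (r = 0.2). The mean error of the estimate was at most 0.5 points, against a Monte Carlo error of about 9/√400 = 0.45.

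**5. Effect on power.** If 45 is the residual SD of the visit-slope model, pairwise power is 0.908 at +1.4% and 0.895 at +3.7%. Minimum MCP-Mod power is 0.921, 0.917, 0.901 and 0.872 at +1%, +2%, +5% and +10%. If 45 is instead the unadjusted SD, then at r = 0.3 pairwise power is 0.915 without EASI and 0.938 with visit slopes. With one slope it is about 0.921 (SE = 9.0·9.40/9.51 = 8.90; 30/8.90 − 1.96 = 1.41).

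**The case against.** The strongest reply is that a single slope is a legitimate, prespecified choice and that nothing in the documents shows it to be costly. No correlation between baseline EASI and percent change is given at any visit. The endpoint is already scaled by its baseline, and IGA-by-visit is already in the model, so what matters is the correlation left after IGA. In the simulated scenarios the single slope was never worse, by model SE, than leaving baseline EASI out. The continuous sensitivity analyses are ANCOVAs with the baseline value (SAP 4.7.1.3), run for week 24 only (SAP 4.7), so they use a week-24 slope and would reveal a material discrepancy.

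Most of this stands, and it is why the point is minor. Two things remain. The ANCOVAs are sensitivity analyses, and the primary contrast keeps the pooled slope. Also, the comparison with omitting EASI depends on the correlation structure: under constant 0.7 the pooled slope is worse than no adjustment (+8.4% against +4.8% at r = 0.3).

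A reader might infer three stronger points that the documents do not support.

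- **That the SAP departs from the synopsis.** The only baseline term in the synopsis model is IGA severity, Protocol 9.1.5.2.1 names baseline IGA in the same sentence, and the SAP keeps that interaction. The protocol has no baseline EASI term, so the SAP dropped nothing.
- **That the primary estimate is biased.** With complete data, randomization protects the contrast. Data after rescue are set to missing, and one assumed two-arm scenario, without IGA and with dropout depending on arm and baseline, moved the estimate by 1.1–1.6 points of 30 for r = 0.2–0.3. That shows a possibility only.
- **That the trial is underpowered.** Minimum MCP-Mod power stays at or above 90% up to about +5%.

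**Conclusion.** The point holds as a minor, low-cost improvement. The SAP text gives baseline EASI one slope for eight visits, and if the true slope changes over time the week-24 contrast is less precise than it could be. The loss is about 0–1%, 1–4% or 3–8% of the standard error for an assumed week-24 correlation of 0.1, 0.2 or 0.3. The full simulated model gives 0.1%, 1.4% and 3.7%. If the slope does not change over time, nothing is lost.

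These figures rest on assumed correlations, visit SDs of 25 to 45 and a relation that grows from near zero at week 1. Only a loss beyond about 5% would take the minimum MCP-Mod power below 90%, and only if 45 is read as the fully adjusted residual SD.

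**What to change.** In SAP 4.7.2, add the interaction of the baseline value of the response with visit to the primary MMRM, and state that it carries over to every continuous endpoint analyzed the same way. If one slope is intended, say so and give the reason.

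**Cost.** In the primary model one slope becomes eight, so the fixed effects rise from 41 (32 treatment-by-visit means, 8 IGA-by-visit, 1 slope) to 48, with 200 subjects. The covariance model is unchanged. DLQI (weeks 2, 12, 24) needs 2 extra parameters and HADS (weeks 12, 24) needs 1. The change should be made before unblinding and recorded in SAP 4.11.

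The synopsis wording could also be aligned with Protocol 9.1.5.2.1 by naming IGA as the baseline that varies by visit. That is editorial only.

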6.1.4 Randomization number

A randomization number will be allocated to each eligible subject at baseline by the IRT system. Randomization will be stratified by baseline IGA score (3 or 4).

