3 INVESTIGATIONAL PLAN

3.1 Overall Study Design and Plan

This is a randomized, placebo-controlled, double-blind, parallel-group, dose-ranging, phase 2b study to evaluate the efficacy and safety of various doses of nemolizumab in moderate-to-severe AD subjects with severe pruritus. The duration of this clinical trial is up to 36 weeks for a given subject, including a 2 to 4-week run-in period, a 24-week treatment period and an 8 week follow-up period (12 weeks after the last study drug administration).

Eligible subjects must have moderate-to-severe AD, severe pruritus and a documented history of inadequate response to topical AD medications. Subjects meeting the inclusion/exclusion criteria at the screening visit will receive background therapy of AD (including a moisturizer, a medium potency TCS for the body, and a low potency TCS for the face, neck etc.) to be used throughout the study. Subjects who still meet the inclusion/exclusion criteria at the baseline visit will be randomized in a 1:1:1:1 ratio to either of the 3 groups of nemolizumab or placebo. Randomization will be stratified by AD severity based on the baseline Investigator's Global Assessment (IGA) scores (3 or 4). Injection of study drug will occur every 4 weeks (Q4w, at weeks 4, 8, 12, 16 & 20). A loading dose will be administered on day 1 for the groups of 10 mg and 30 mg only (20 mg and 60 mg, respectively), while for 90 mg group, the same dose will be administered at each injection visit.

An independent Data Monitoring Committee (IDMC) will be set-up to monitor safety data generated in this clinical trial on an ongoing basis and make appropriate recommendations to the sponsor.

Assessments of efficacy, safety and PK will be conducted throughout this clinical trial. Refer to Appendix 1 for the complete schedule of assessments.

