4.7.3 Secondary Efficacy Endpoints

For analyses up to week 24 using the MMRM approach for continuous endpoints, only data collected up to week 24 will be included in the model.

4.7.3.1 Proportion of subjects achieving IGA success (defined as IGA 0 [clear] or 1 [almost clear]) at each visit up to week 24

A CMH test stratified by baseline IGA severity (3, 4) will be used to test the difference between each nemolizumab regimen and the placebo for the proportion of subjects achieving certain “success” at a given visit for ITT and PP populations. A 95% CI for the treatment difference will be calculated.

A bar chart and line plots will be produced over time for each treatment group to summarize the data (“responders”).

Sensitivity analysis: Sensitivity analyses will be performed as described in 4.7.1.3.

Subgroup analysis: Subgroup analyses will be investigated as described in 4.7.1.6.

Logistic regression will be used with response status as the dependent variable and treatment group, subgroup factor and interaction between treatment group and subgroup as independent variables. Odds ratios and the respective 95% CIs will be used for all subgroup comparisons. In addition, the p-values for the interaction of the treatment groups and the subgroups will also be provided, wherever appropriate.

4.7.3.2 Proportion of subjects achieving IGA success (defined as IGA 0 [clear] or 1 [almost clear]) and a reduction of at least 2 points at each visit up to week 24

This endpoint will be analyzed as described in section 4.7.3.1.

4.7.3.3 Percent change from baseline in EASI at each visit up to week 24

This endpoint will be analyzed as the primary efficacy endpoint using a MMRM approach for ITT and PP populations.

4.7.3.4 Absolute and percent change from baseline in weekly average of the peak and average pruritus NRS at each visit up to week 24

The following endpoints will be analyzed as the primary efficacy endpoint using a MMRM approach for ITT and PP populations.

- Absolute change from baseline in weekly average of the peak pruritus NRS at each visit up to week 24
- Percent change from baseline in weekly average of the peak pruritus NRS at each visit up to week 24
- Absolute change from baseline in weekly average of the average pruritus NRS at each visit up to week 24
- Percent change from baseline in weekly average of the average pruritus NRS at each visit up to week 24

The plots showing the changes over time within each treatment group will be provided.

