4.10 Determination of Sample Size

Sample size is estimated using MCP-Mod approach by selecting a set of candidate dose response shapes based on EASI response in previous Phase 2a study (CIM003JG study report 2017). Refer to Section 4.7.2 on the models considered as candidates in the estimation of sample size.

Assuming a placebo response of 35%, standard deviation 45% and a maximum treatment difference of 30%, in terms of percent change from baseline in EASI, 50 subjects per arm will provide at least 90% power to detect a statistically significant dose-response for at least one model at 1-sided significance level of 0.025.

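### The subgroup models leave out the IGA randomisation stratum, and the week-24 subgroup ANCOVA has no stated rule for missing values

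*SAP*

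**What the plan says.** Protocol 6.1.4 stratifies randomisation by baseline IGA (3 or 4). SAP 4.7.1.2 names baseline IGA and baseline EASI as covariates of the primary analysis. The primary MMRM in SAP 4.7.2 is specified as "including terms of treatment group, and baseline IGA severity for ITT and PP populations", with treatment and IGA effects varying by visit and the baseline value as a covariate. The sensitivity ANCOVA in 4.7.1.3 and the CMH test in 4.7.3.1 also keep IGA.

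The subgroup models are listed differently:

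- Percent change in EASI (4.7.2): "ANCOVA including terms of treatment group, the corresponding baseline value, subgroup factor and interaction between treatment group and subgroup". Section 4.7.3.4 applies the same method to percent change in peak pruritus NRS.
- Binary endpoints (4.7.3.1): "Logistic regression will be used with response status as the dependent variable and treatment group, subgroup factor and interaction between treatment group and subgroup" as the independent variables.

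SAP 4.7 restricts subgroup analysis to week 24. SAP 4.7.1.3 sets efficacy data after rescue to missing, except in the Observed Case analysis. For continuous endpoints it assigns MMRM to the primary analysis and five other approaches to the sensitivity analyses. Missing binary outcomes count as non-response. It names no method for the continuous subgroup analyses. Protocol 9.1.4 lists the subgroups without a model.

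**The concern.** SAP 4.7.1.6 gives the purpose of the subgroup work as judging whether treatment effects are consistent. That judgement is easiest when subgroup and overall estimates come from the same kind of model on the same effective sample. Two features stand in the way.

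First, the stratum is absent from both subgroup models, and the SAP gives no reason. In the logistic model this leaves no adjustment for baseline severity unless IGA or EASI is the subgroup. For IGA success the stratum is directly prognostic: a subject starting at 4 must drop at least 4 - 1 = 3 grades, a subject starting at 3 at least 3 - 1 = 2. Stratified randomisation balances IGA overall, not within levels of region, age, race or AD type. Omitting a prognostic factor also shrinks odds ratios towards 1.

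Second, the continuous subgroup analysis moves from an MMRM, which uses earlier visits of subjects with no week-24 value, to a single-visit model with no missing-data rule. If placebo subjects doing badly are rescued more often, deleting their later values flatters placebo. A subgroup estimate could then sit below the overall one with no heterogeneity at all. The trial is meant to support dose selection for Phase 3 (SAP 1), so these displays will be read.

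**Working it through.** **The plan's own figure.** SAP 4.10 states "Assuming a placebo response of 35%, standard deviation 45% and a maximum treatment difference of 30" percent, and that "50 subjects per arm will provide at least 90% power" to detect a dose response "for at least one model at 1-sided significance level of 0.025". Inputs: doses 0/10/30/90 mg, the nine listed shapes scaled to 30 points at 90 mg, optimal contrasts, df = 4 x 50 - 4 = 196, and 400,000 draws. The critical value is 2.251. Power runs from 92.9% (Emax, ED50 10 mg) to 98.3% (sigmoid, ED50 20 mg, Hill 4). A simple two-arm comparison has 91.5% power and needs 48 per arm for 90%. The stated figure reproduces, and nothing in this point changes it.

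**Where IGA appears.**

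| Analysis | SAP | IGA stratum | Missing week-24 values |
|---|---|---|---|
| Primary MMRM | 4.7.2 | yes | handled by the MMRM |
| Sensitivity ANCOVA | 4.7.1.3 | yes | five named approaches |
| CMH, binary | 4.7.3.1 | yes | non-responder |
| Subgroup ANCOVA | 4.7.2, 4.7.3.4 | only if it is the subgroup | not stated |
| Subgroup logistic | 4.7.3.1 | only if it is the subgroup | non-responder |

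**Size if the ANCOVA is run without imputation.** The documents give no rescue or dropout rate, so every rate here is assumed. Simulation: one dose against placebo, 50 per arm, true week-24 difference 30 points in favour of active, SD 45, six visits (weeks 4 to 24) with correlation 0.7 between adjacent visits. Forty percent have IGA 4; the IGA effect is 0, 10 or 20 points; mean baseline EASI is 10 points higher in IGA 4. Loss at each visit depends on the last observed EASI change. There are 3,000 runs per setting and no subgroup split. Ranges cover the three IGA effects; entries are mean differences in points.

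| Missing, placebo / active | ANCOVA without IGA | ANCOVA with IGA | MMRM with IGA |
|---|---|---|---|
| 0 / 0 | 29.92-30.22 | 29.99-30.25 | 29.99-30.25 |
| 13-14% / 9-10% | 29.24-29.31 | 29.25-29.32 | 29.89-29.95 |
| 28-32% / 19-22% | 28.05-28.23 | 28.16-28.26 | 29.90-30.17 |
| 44-50% / 31-36% | 26.22-26.91 | 26.50-26.99 | 30.02-30.23 |

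Monte Carlo error of a mean is about 9.66/sqrt(3000) = 0.18 to 12.16/sqrt(3000) = 0.22 points.

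- Shortfall of the ANCOVA without IGA against the MMRM in the same runs: 0.6-0.7 points in the second row (29.89 - 29.30 = 0.59; 29.95 - 29.24 = 0.71), 1.8-2.1 in the third, and 3.2-3.8 in the fourth (30.11 - 26.91 = 3.20; 30.02 - 26.22 = 3.80).
- Effect of adding IGA to the ANCOVA: at most 26.50 - 26.22 = 0.28 points on the mean and 11.42 - 11.30 = 0.12 on its SD. Even at 20 points, IGA carries only 0.4 x 0.6 x 20^2 = 96 of 96 + 45^2 = 2,121 units of variance (4.5%), and baseline EASI already picks up part of that.

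**Set against subgroup precision.** The 95% half-width for one dose against placebo is 1.96 x 45 x sqrt(2/m), with m subjects per arm. For a subgroup holding half the subjects, m = 25 x (1 - missing):

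| Missing | m | Half-width |
|---|---|---|
| 10% | 22.5 | 26.3 |
| 20% | 20 | 27.9 |
| 30% | 17.5 | 29.8 |
| 40% | 15 | 32.2 |

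The shortfall is therefore small beside the uncertainty: roughly 0.6/26.3 = 2% to 3.8/32.2 = 12% of the half-width.

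**The case against.** A reader might infer that the subgroup analysis is confined to unrescued completers. The SAP does not say so. It is silent on missing values here, and it elsewhere pairs ANCOVA with imputed data (4.7.1.3), so an imputed analysis is a possible reading. The one unimputed analysis it defines, Observed Case, keeps post-rescue values. Even with no imputation, completers would be the wrong word: subjects who stop study drug stay in the study (Protocol 6.1.8.2), and early-termination or unscheduled values on days 156-183 are slotted to week 24 (SAP 4.2). What stands is that no method is named, and that the listed terms fitted to the data as defined would use unrescued observed values only.

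A reader might also infer that every subgroup difference is pulled towards zero, or that the interaction tests are biased. Neither was shown. A shortfall common to all subgroup levels largely cancels from an interaction contrast; only missingness that differs between levels would disturb it. Nor do moderate rates produce a loss of many points: the shortfall exceeds 3 points only with 44-50% of placebo missing. The simulated loss depends only on observed values, which is the setting where MMRM is unbiased, so the comparison favours the MMRM by design.

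The precision argument for IGA is weak in the EASI ANCOVA, as the figures show. For peak pruritus NRS the baseline term is the NRS score rather than EASI, and that case was not simulated. The logistic model loses no subjects.

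Finally, a simpler model for sparse subgroups is defensible. A treatment-by-subgroup-by-visit MMRM for race has 4 x 8 x 4 = 128 cell means for about 200 subjects, against 4 x 4 = 16 for the week-24 ANCOVA, and the SAP already plans for non-convergence of the smaller MMRM. This argues against insisting on the MMRM everywhere, but not against naming a missing-data method or adding the stratum.

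**Conclusion.** The point holds in two parts. The omission of IGA from both subgroup models is plain from the text. It matters mainly in the logistic model, where no size can be given because the documents state no response rates by IGA. In the EASI ANCOVA it is worth 0.3 points or less under the assumed inputs.

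The missing-data part is conditional. If the subgroup ANCOVA is run as listed with no imputation, it is not on the same footing as the primary MMRM, and a true 30-point difference would appear as roughly 26 to 29 points across the assumed missingness range. That rests on outcome-dependent rescue, a visit correlation of 0.7 and an SD of 45 at every visit. With no missing data the two methods agree.

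The subgroup analyses are exploratory (SAP 4.7.1.6). The primary inference, the MCP-Mod test and the sample size are untouched. This is an inexpensive specification gap worth closing before database lock, not a threat to the trial's conclusion.

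**What to change.** In SAP 4.7.2, 4.7.3.1 and 4.7.3.4, add baseline IGA to the subgroup ANCOVA and the subgroup logistic model, except where IGA is the subgroup.

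Name one missing-data method for the subgroup ANCOVA. The simplest is to run it on the multiple-imputation data sets already planned in 4.7.1.3. State whether the imputation model carries the subgroup factor and its interaction with treatment; if not, imputed values will tend to understate any interaction. Where cell sizes allow, the primary MMRM with subgroup interactions is an alternative that lines up directly with the overall estimate.

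The cost is SAP wording, some programming and, for sparse subgroups, pooling, which 4.7.1.6 already permits. No data collection or sample size changes.
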